
## VULVODYNIA

Vulvodynia is a condition that occurs in 8-10% of women of all ages (Arnold et al., 2007; Harlow et al., 2014) and is characterized by localized pain in the vulva, either spontaneous or upon touch, and can occur during sexual and/or non-sexual situations (Bergeron et al., 2020). Vulvodynia has a negative effect on the quality of life of women and their partners and imposes a profound personal and social economic burden. The diagnosis is established through a careful history and pelvic examination, including the cotton swab test, based on persistent vulvar pain lasting more than 3 months without an identifiable cause and with several potential associated factors. These include musculoskeletal and neurological factors, comorbid pain syndromes (such as fibromyalgia, chronic migraine, and irritable bowel syndrome) and psychosocial factors (Reed et al., 2012; Wesselmann et al., 2014; Bergeron et al., 2020). Current literature suggests that the onset and maintenance of vulvodynia likely involves a complex interplay of peripheral and central pain mechanisms, pelvic floor muscle and autonomic dysfunction, anxiety, depression, and adverse childhood events, as well as cognitive-affective, behavioral, and interpersonal factors (Bergeron et al., 2020). Vulvodynia has traditionally been conceptualized in a dualistic manner, arising from either physical factors or psychological and sexual difficulties, although research contrary to this concept and other hypotheses suggest that these two perspectives should be combined. Therefore, future studies should move in this direction, seeking to identify specific pathophysiological mechanisms within the framework of a biopsychosocial model. Indeed, a more recent theorization has focused on an integrated model that considers the interdependence of biopsychosocial factors in vulvodynia and associated disorders, in which medical and psychosocial mechanisms are considered to contribute to the onset, chronicization and exacerbation of pain and associated difficulties (Bergeron et al., 2011). The neurophysiology of vulvodynia is multifaceted and is characterized by both peripheral and central sensory abnormalities (Wesselmann et al., 2014; Pukall et al., 2016). Furthermore, increased sensitivity to different sensory modalities at extragenital sites has been demonstrated in women with vulvodynia (Giesecke et al., 2004; Foster et al.,

2005; Sutton et al., 2015), suggesting central sensitization. This central sensitization could explain the observation of overlapping chronic pain conditions in women with vulvodynia, which need further investigation to be better understood.

### PSYCHOLOGICAL FACTORS ASSOCIATED TO NP

As we have already pointed out separately for the three pathological conditions (chronic migraine, fibromyalgia, and vulvodynia), there is evidence that factors such as personality traits, defense mechanisms, central sensitization, and childhood traumatic experiences may contribute significantly to the genesis of these disorders through a process of central sensitization of pain pathways. Central sensitization (CS) is defined as increased responsiveness of nociceptive neurons in the central nervous system to their normal or subthreshold afferent input according to the IASP - International Association for the Study of Pain (Arendt-Nielsen et al., 2018). A sensitized nervous system has been considered one of the most important mechanisms involved in NP (Cohen, 2022). CS plays a role in fibromyalgia, in which alteration of central nociceptive processing occurs and pain can be worsened by psychological factors (Sluka & Clauw, 2016). In migraine, CS may contribute to acute allodynia and headache chronification (De Tommaso & Sciruicchio, 2016). Furthermore, in migraine CS may play a role in trigeminal nerve activation and cortical spreading depression (De Tommaso & Sciruicchio, 2016). It has been suggested that migraine may be considered as a brain state of altered excitability and a disorder of sensory processing (Goadsby et al., 2017), encompassing additional symptoms as fatigue and mood disorders (Karsan & Goadsby, 2021). Structural and functional MRI studies in women with provoked vulvar or distant/extra-genital pain have supported a role of central sensitization and dysregulation of endogenous pain modulatory systems in the central nervous system in the pathophysiology of vulvodynia (Bergeron et al., 2020).

In the process of central sensitization, psychological factors such as traumatic events in childhood, the development of specific personality expressions (traits), and the use of different forms of defense mechanisms also play a role. No study to our knowledge has yet tried to identify specific clusters of psychological factors (personality traits, defense mechanisms, central sensitization, and childhood traumatic experiences) capable of characterizing or differentiating between the different pathologies expressed by a NP.

In addition to this, the study of psychosocial factors associated with the experience of such pathologies or possible emerging clusters such as depression, anxiety, somatization, quality of life, alexithymia, social support, sexual satisfaction, and functioning. This will make it possible to identify specifically for each condition the areas of greatest interest that can be investigated and treated in clinical intervention tailored to the person.

### Aims

The first aim of this study is to highlight possible psychosocial clusters of variables that are specific to the onset and maintenance for each condition (FM, CM, and VU). Specifically, the observation of possible clusters will be made based on variables such as personality traits, defense mechanisms, central sensitization, and childhood traumatic experiences. The hypothesis is that specific psychological factors (clusters of high number of early traumatic events, high levels of central sensitization, and specific traits and defense mechanisms) characterize FM, CM, and VU groups compared to controls reporting other types of CP (e.g., knee arthrosis, rheumatoid arthritis).

A second aim, to give directions for tailored psychological treatments devoted to these conditions, is to explore the association between FM, CM, and VU with depression, anxiety, somatization, quality of life, alexithymia, social support, sexual satisfaction, and functioning. In line with our hypothesis that each of

these conditions has specific areas of psychological sensitivity, this will make it possible to identify specifically for each condition the areas of greatest interest that can be investigated and treated in clinical intervention.

## Methods

### *Participants*

The study involves the collection of data from a self-administered questionnaire in several Italian centers specializing in the above-mentioned clinical conditions under the guidance of the research team of the Department of Dynamic and Clinical Psychology and Health Studies, PI [name].

The four centers involved in the recruitment of the participants will be the Università di Milano IRCCS Sant'Ambrogio Galeazzi under the head of [name] and Dott. [name], the IRCCS Mondino di Pavia under the head of [name] and [name], The Policlinico San Matteo of Pavia under the head of [name] and Dott. [name], and the Policlinico Umberto I of Sapienza University of Rome under the head of Dott. [name].

Questionnaires will be accessible online through a web survey available on the Google.forms platform. Participants will provide an informed consent before accessing the survey, and the questionnaire will be anonymous with no remuneration provided. The institutional ethics committee of the Dept. of Dynamic, Clinical and Health Psychology, Sapienza University of Rome, Italy (protocol code 0001979) approved the study on 25th November 2022 [UOR: SI000092 - Classif. VII/15].

#### *Inclusion criteria:*

- age range 18-65 years
- education > 5 years
- diagnosis of FM according to Wolfe, 2016
- diagnosis of CM according to Olesen, 2017
- diagnosis of VU according to Bornstein et al., 2016

#### *Exclusion criteria*

- severe psychiatric disorders and/or cognitive impairment
- difficulties in comprehension/expression in Italian
- history of other chronic pain disorder(s)
- history of other neurological disorders besides migraine

## MEASURES

The study involves the administration of a protocol of self-report questionnaires consisting of two parts: the main (about 25 minutes for the administration) and the optional one (additional 20 minutes). This decision stems from the realization of the length of the protocol, to increase the collection of data in pursuit of the main objective of the study (cluster analysis).

### *Self-report questionnaires*

#### *Main questionnaires (all the participants are requested to complete them)*

- Highly Sensitive Person Scale (HSP-12) (Aron & Aron, 1997; Lionetti et al., 2018): this questionnaire investigates the theoretical framework of Sensory Processing Sensitivity, referring to a temperamental trait that predisposes to a broader sensory processing of information captured by a variety of indicators, rather than simple sensitivity to sensory stimuli. The questionnaire reports a total sensitivity score and 3 sub-factors (Easy of Excitation (EOE), Aesthetic Sensitivity (AES) and Low Sensory Threshold (LST)).
- Central Sensitivity Inventory (CSI) (Chiarotto et al., 2018): The Central Sensitisation Inventory was developed to assess the overlapping symptomatic dimensions of the central sensitivity syndrome. This measure is intended as a screening tool to help identify the presence of the syndrome and to alert clinicians that presenting symptoms may be related to it. It consists of two parts: part A provides a 0-100 total score for 25 items on current health symptoms with five response options ranging from 'never' (0) to 'always' (4); part B investigates if patients were previously diagnosed by a physician with one or more of seven different conditions.
- Traumatic Experiences Checklist (TEC) (Nijenhuis et al., 2002): the instrument investigates 29 types of potential trauma, including the events listed in criterion A of PTSD, as well as other potentially overwhelming events: loss of significant others, life-threatening illness or aggression, experience of warehousing, emotional neglect, emotional abuse, physical abuse, sexual harassment and sexual trauma. The questionnaire includes a total complex trauma score and 5 subscales investigating emotional neglect, emotional abuse, physical threat, sexual harassment, and sexual abuse.
- PID-5 Short form (Thimm et al., 2016): This instrument represents the short version of the PID-5 self-report inventory designed to assess the 25 facets of pathological personality traits and the five higher-order domains of DSM-5 Criterion B. It assesses 5 personality trait domains including negative affect, detachment, antagonism, disinhibition, and psychotism, with each trait domain consisting of 5 items.
- Defense Mechanism Rating Scales - DMRS-SR-30 (Di Giuseppe et al., 2020); is an instrument based on the identification of 30 individual defenses arranged hierarchically in 7 levels according to similarity of function and level of adaptability. The DMRS provides a definition of each defense mechanism, a description of its intrapsychic function and criteria for discriminating one defense from its neighboring defenses. Defense levels can be categorized as mature and immature neurotic, and the latter is further subdivided into depressive and non-depressive.
- Mental Pain Questionnaire (Svicher et al., 2019): is a 10-item true-false style self-report questionnaire developed to assess mental pain.

#### *Optional questionnaires (the participant decides whether to complete them)*

- Brief Symptom Inventory (BSI-18) (Franke et al., 2017): an abbreviated version of Derogatis' Brief Symptom Inventory, contains the three six-item scales of Somatization, Depression, Anxiety and the Global Symptom Score (GSI).
- SF-12 - Quality of Life Assessment (Apolone et al., 2001): The SF-12 is a generic short-form health survey developed in the United States from the original SF-36. It produces two summary measures for the assessment of self-perceived physical and mental health that are interchangeable with those of the SF-36.

- Toronto Alexithymia Scale (TAS-20) (Bagby et al., 1994): The Toronto Alexithymia Scale is a 20-item self-administered questionnaire that measures difficulty in identifying and describing emotions, which is an important part of alexithymia.
- Chronic Pain acceptance Questionnaire (CPAQ-8) (Fish et al., 2010): is an 8-item inventory measuring the acceptance of chronic pain.
- SPQ - Social Support Questionnaire (SPQ) (van der Lugt et al., 2012): is a short measure of perceived social support in relation to pain.
- Sexual Satisfaction Scale (SSS) - Short form) (Meston & Trapnell, 2005): represents a short 6-item measure of sexual satisfaction and discomfort.
- Short Form McGill Questionnaire (SF-MGQ) - Adapted for genito-pelvic pain (Melzack & Raja, 2005). Represents a qualitative and quantitative measure of pain, adapted to the genito-pelvic area.
- Female Sexual Function Index (FSFI) (optional) and International Index of Erectile Function (IIEF) (optional) (Rosen et al., 1997; 2000): represents a differentiated questionnaire for females and males on sexual function (desire, arousal and orgasm and satisfaction).

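### All eight Aim 2 domains are measured only in the optional questionnaire block, and the analysis plan makes no provision for selective completion

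*Combined protocol and SAP*

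**What the plan says.** The Aims section sets the second aim as to "explore the association between FM, CM, and VU with depression, anxiety, somatization, quality of life, alexithymia, social support, sexual satisfaction, and functioning", with the stated purpose of directing tailored psychological treatment for each condition.

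The MEASURES section splits the survey into a main part of about 25 minutes and an optional part of 20 more. It says that this was done because of the survey's length and "to increase the collection of data in pursuit of the main objective of the study", namely the cluster analysis. For the optional part, "the participant decides whether to complete them".

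The instruments for Aim 2 are all listed in that optional part: BSI-18 (depression, anxiety, somatization), SF-12, TAS-20, the pain-related social support questionnaire, the short sexual satisfaction scale, and FSFI or IIEF. The last two are marked optional a second time.

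The main part, which all participants are asked to complete, holds HSP-12, CSI, TEC, PID-5, DMRS-SR-30 and the Mental Pain Questionnaire. The last of these "is a 10-item true-false style self-report questionnaire developed to assess mental pain".

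The planned statistical analyses mention selection bias once, when groups are compared on sociodemographic characteristics to choose covariates. For the other psychological domains, the nearest analysis is a Pearson correlation with the clusters. Nothing is said about people who skip the optional block.

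**The concern.** A participant who has just spent 25 minutes on the main questionnaires chooses whether to spend 20 more. The protocol itself associates these conditions with fatigue, cognitive problems, anxiety and depression. These are plausible reasons to stop, and some of them are what Aim 2 measures.

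If the link between distress and stopping differs between groups, or if completion rates differ, completers can show a difference that the recruited groups do not have, or hide one that they do. A larger sample does not remove this. Because Aim 2 is meant to point treatment at each condition's areas of sensitivity, such an error would pass directly into its conclusions.

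The survey is anonymous and no recontact is described, so skipped answers are probably lost.

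**Working it through.** **Mapping.** Aim 2 names eight domains. BSI-18 covers three. SF-12, TAS-20, the social support questionnaire and the sexual satisfaction scale cover one each. Functioning is covered by FSFI/IIEF, or by SF-12 if general functioning is meant. All of these are optional, and no main-block instrument is described as measuring any of the eight.

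**The plan's sample size.** Inputs from the planned statistical analyses: 4 groups, alpha 0.05, power 85%, effect size 0.35 (read as Cohen's f). With a non-central F, λ = f²N and 3 and N − 4 degrees of freedom, 27 per group (108 in total) gives λ = 0.1225 × 108 = 13.23 and power 0.863. The plan's 108 therefore matches the total, whereas the plan states 108 per group (432). That is a separate matter. The rest of this check takes 432 as stated.

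**Power after skipping** (completion rates are assumptions; the documents give none):
- 60%: 108 × 0.6 ≈ 65 per group, N = 260, λ = 31.85, power above 0.99.
- 40%: 108 × 0.4 ≈ 43 per group, N = 172, λ = 21.07, power 0.98.
- 25%: 27 per group, N = 108, power 0.86.

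**Bias with no true difference.** Let distress Y be standard normal in every group and let logit Pr(complete) = a + ln(OR) × Y, with a chosen so that a fraction c completes. The completer mean is m = E[Y × Pr(complete | Y)] / c. The bias is m in the three conditions minus m in controls; the table gives its absolute size. Rejection rates come from simulating the four-group F test with 108 recruited per group. Completion is 60% or 40%, the same in all groups.

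| OR per SD, conditions / controls | m, conditions (60%; 40%) | m, controls (60%; 40%) | Bias, SD | Rejection |
|---|---|---|---|---|
| 0.5 / 0.5 | −0.251; −0.376 | −0.251; −0.376 | 0 | about 5% |
| 0.67 / 0.8 | −0.154; −0.232 | −0.088; −0.132 | 0.07; 0.10 | about 6–7% |
| 0.5 / 0.67 | −0.251; −0.376 | −0.154; −0.232 | 0.10; 0.14–0.15 | about 8–10% |
| 0.67 / 1 | −0.154; −0.232 | 0; 0 | 0.15; 0.23 | about 13–18% |
| 0.5 / 1 | −0.251; −0.376 | 0; 0 | 0.25; 0.38 | about 28–41% |

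**Unequal completion rates.** As a second check, take a latent-normal model in which the bias in a group mean is −ρφ(z_c)/c, with ρ the correlation of the outcome with non-completion. At c = 0.8 the factor is 0.280/0.8 = 0.350, and at c = 0.6 it is 0.386/0.6 = 0.644. With ρ = 0.3 in both groups, the spurious difference is 0.3 × (0.644 − 0.350) = 0.09 SD. With ρ = 0.5 it is 0.15 SD. Equal dependence on distress is therefore harmless to the null comparison only if completion rates are also similar.

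**What adjustment recovers.** Weighting on a main-block score correlated 0.6 with the outcome cuts a bias of 0.26 SD to 0.17, removing (0.26 − 0.17)/0.26 = 35%. At a correlation of 0.8 it cuts 0.32 to 0.13, removing 59%. At 0.7, roughly half is removed.

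**The case against.** The split is deliberate and disclosed: it protects the main objective, and Aim 2 is worded as exploratory. The controls are also chronic pain patients (knee arthrosis and rheumatoid arthritis are the examples given), so fatigue and distress could make them skip for the same reasons. With the same dependence and the same completion rate in all groups, there is no false-positive inflation. The planned analyses also specify no diagnosis-group test of the Aim 2 outcomes, so the four-group test above is inferred from the wording of the aim.

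Most of this stands, and it limits the size of the point. It does not remove the point. The stated rationale explains why the block is optional but not how its results will be analysed, and selective completion can distort a correlation with clusters as well as a group contrast. Equal dependence is also not entirely harmless: a true difference of 0.5 SD shrinks to about 0.45.

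A reader might also infer that two main-block scales, HSP-12 and the Mental Pain Questionnaire, serve no aim and could both give way to BSI-18. The documents support this for the Mental Pain Questionnaire only. HSP-12 is described as measuring a temperamental trait, Aim 1 gives an open list that includes personality traits, and the count of twenty-two clustering variables can be reached with or without it. It may be a clustering input.

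**Conclusion.** The point holds as a gap in the analysis plan. All eight Aim 2 domains depend on voluntary completion, and nothing in the plan checks or adjusts for who completes.

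The size is unknown. At 40–60% completion, equal across groups, it runs from about 0 (equal dependence on distress), through 0.07–0.15 SD (weaker dependence in controls), to 0.15–0.38 SD (none in controls). Completion rates and slopes are all assumptions.

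Two stronger readings are not supported. A reader might take the top of that range as the expected bias, but it needs controls whose skipping is unrelated to distress, which nothing in the documents suggests. A reader might also infer that Aim 2 would be underpowered. With 432 recruited, power at f = 0.35 is still 0.98 at 40% completion, so the problem is bias and not power.

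**What to change.** Add to the planned statistical analyses:

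1. Report optional-block completion by diagnosis group, and compare completers with non-completers on the main-block scores.
2. Analyse the Aim 2 outcomes with multiple imputation, or with inverse-probability-of-completion weights, built from the main-block scores (CSI, TEC, PID-5, DMRS-SR-30, HSP-12, Mental Pain Questionnaire), age, sex and diagnosis. Show the unadjusted result beside it.
3. State that Aim 2 conclusions are conditional on these variables accounting for who completed the block.

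The cost is a few lines of plan, a little more analysis and slightly wider intervals. Only part of any bias is removed, roughly half at a correlation of 0.7.

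Optionally, if the form can still be changed, exchange the Mental Pain Questionnaire, which no aim names, with BSI-18. This adds 18 − 10 = 8 items to the main block, covers only three of the eight domains, runs against the burden argument, and may need notification to the ethics committee. Recruitment status is not stated, so two form versions could result. Leave HSP-12 where it is.

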#### STATYSTICAL PLANNED ANALYSES

The required sample size was estimated a priori for the ANOVA procedure that tested the cluster model sensitivity having 4 groups (migraine, fibromyalgia, vulvodynia, and controls). Using the G\*power program,  $p = 0.05$ , statistical power of 85%, and effect size of 0.35, the calculation yielded a total sample size of  $n = 108$  participants per group (432 as total) The four centers involved in the recruitment of the participants will be the Università di Milano IRCCS Sant'Ambrogio Galeazzi under the head of [name] and Dott. [name], the IRCCS Mondino di Pavia under the head of [name] and [name], The Policlinico San Matteo of Pavia under the head of [name] and Dott. [name], and the Policlinico Umberto I of Sapienza University of Rome under the head of Dott. [name].

ANOVAs and  $\chi^2$  analyses will be carried out to compare groups on sociodemographic characteristics for descriptive reasons and to select possible covariates based on selection bias.

A group of cluster analyses will be performed to classify the samples based on personality traits, defense mechanisms, central sensitization, and childhood traumatic experiences (twenty-two variables corresponding to total scores and thematic subscales of the related measures), aiming to identify different clinical phenotypes within the study samples. A statistical procedure of Two-Step Cluster Analysis will be preferred due to its ability to ensure that one variable does not dominate the cluster solution. Furthermore, it enables the user to identify the importance of each item in the cluster solution. The model fit will be assessed by Schwarz's Bayesian Information Criterion and evaluated by the average silhouette coefficient, an internal validity index representing cluster cohesion and separation quality, ranging between 0 and 1; the closer to 1, the better the model.

Crosstab analyses will be performed to test the association and their strength, and MANOVAs to detect differences in the classification variables based on cluster groups, and Pearson's correlation to explore associations among clusters and other psychological domains. The statistical analyses will be performed using IBM SPSS v. 27.0 and AMOS v.22 (SPSS Inc., Chicago, IL, USA).

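### The study is sized on an ANOVA across the four diagnoses, but no listed analysis compares the diagnoses on trauma, sensitization, traits or defenses

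*Combined protocol and SAP*

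**What the plan says.** The Aims section states a hypothesis about diagnoses: early trauma, central sensitization, and particular traits and defenses "characterize FM, CM, and VU groups compared to controls reporting other types of CP". The section on psychological factors presents the novelty of the study as finding clusters "capable of characterizing or differentiating between the different pathologies expressed by a NP".

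The statistical section (headed STATYSTICAL PLANNED ANALYSES) takes the four diagnoses as the groups for its sample size: "The required sample size was estimated a priori for the ANOVA procedure that tested the cluster model sensitivity having 4 groups". The inputs are alpha 0.05, power 85% and effect size 0.35. The result is 108 "participants per group (432 as total"). The outcome of that ANOVA is not named.

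The analyses then listed are:
- ANOVA and chi-square tests to "compare groups on sociodemographic characteristics for descriptive reasons and to select possible covariates based on selection bias";
- Two-Step clustering on 22 totals and subscales;
- crosstabs, with neither margin named;
- "MANOVAs to detect differences in the classification variables based on cluster groups";
- Pearson correlations between clusters and the other psychological domains.

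The MEASURES section describes cluster analysis as the main objective.

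**The concern.** The hypothesis and the sample size are both framed by diagnosis, while every named test on the psychological scores is framed by cluster. If the plan is followed as written, the hypothesis has no direct test and the quoted power belongs to no listed analysis.

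Two things are at stake. First, a significant cluster-by-diagnosis table shows that the cluster mix differs between diagnoses. It does not show which trauma, trait or defense score differs in which condition, and that is what the Aims ask. The MANOVAs by cluster do not fill this gap, because they test the variables that formed the clusters and so find differences that are largely built in. Second, unsupervised clusters tend to follow the largest shared variation among the scales, such as overall severity. A difference confined to a few scores in one condition may then not show in the table. A comparison by diagnosis added after the data are seen would be post hoc.

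**Working it through.** **1. Matching hypothesis to analyses**

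| Analysis | Grouping factor | Outcome |
|---|---|---|
| Sample-size ANOVA | Four diagnoses | Not named |
| ANOVA / chi-square | Study groups | Sociodemographics only |
| Crosstabs | Not named | Not named |
| MANOVAs | Cluster | The classification scores |
| Pearson correlations | Cluster | Other psychological domains |

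No row combines diagnosis with the Aim 1 scores. The second aim has the same gap: it is stated by diagnosis but analysed by cluster.

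**2. The plan's own sample size**

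One-way ANOVA F test with k = 4, df = (3, N - 4) and noncentrality lambda = f^2 x N. The metric of 0.35 is not named; I read it as Cohen's f.

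- N = 104 (26 per group): lambda = 0.1225 x 104 = 12.74, power 84.8%.
- N = 108 (27 per group): lambda = 0.1225 x 108 = 13.23, power 86.3%.
- N = 432: lambda = 0.1225 x 432 = 52.92, power above 99.9%.

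The stated inputs therefore give 108 in total, not 108 per group. The figure 432 is 4 x 108. Reading 0.35 as a standardized difference (f = 0.175) gives 408, which does not match either.

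**3. What 432 supports for a direct comparison by diagnosis, at 85% power**

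- Alpha 0.05: f = 0.170 (lambda = 12.4).
- Alpha 0.05/22: f = 0.224 (lambda = 21.6).
- At alpha 0.05/22 and f = 0.35, 184 in total (46 per group) would be enough.

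**4. What 432 supports for a cluster-by-diagnosis crosstab**

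Chi-square test with df = 3(c - 1) for c clusters, lambda = N x w^2, alpha 0.05, power 85%:

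| Clusters | df | lambda | w = sqrt(lambda/432) |
|---|---|---|---|
| 2 | 3 | 12.30 | 0.169 |
| 3 | 6 | 15.25 | 0.188 |
| 4 | 9 | 17.45 | 0.201 |

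The plan gives none of these.

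**5. Crosstab against direct tests, by simulation**

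Assumed: 4 x 108 participants, 22 normal scores that share a common factor, and clustering methods that approximate Two-Step (likelihood-based, with k-means as a check). Most scenarios used 60 to 120 data sets, some as few as 20. Monte Carlo error is about 5 points at 100 data sets and larger with fewer. For one raised group out of four, f = d x sqrt(3)/4, so f = 0.17 and 0.35 correspond to d = 0.39 and 0.81 SD.

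| Assumed pattern | Crosstab p < 0.05 | Bonferroni ANOVAs by diagnosis, at least one significant |
|---|---|---|
| No difference | 3-10% | 4% |
| 1-2 own scores per condition, f = 0.17-0.35, BIC-chosen clusters | 3-13% | 88-100% |
| 3 own scores, 0.35-0.5 SD | 3-18% | about 93-100% |
| 4 own scores, f = 0.35, loading 0.55 | 42% | 100% |
| 7 own scores, f = 0.35, loading 0.55 | 86% | 100% |
| Trauma and sensitization raised in all three conditions, plus own traits/defenses, 0.35 SD | 39-50% | 97-100% |
| Same pattern, 0.5 SD | 64-84% | 97-100% |
| All 22 scores raised, 0.35 SD or more | 99-100% | 97% at 0.35 SD |

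The k-means check gave about 45-99% for the shared pattern over 0.35-0.5 SD. A MANOVA by diagnosis reached 99-100% in the 1-2 score setting. With uncorrelated scores and 1-2 own scores per condition, BIC chose a single cluster every time, so there was no crosstab to test. Forcing 2-4 clusters then gave 16-96%.

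**The case against.** The sample-size sentence does name a four-diagnosis ANOVA, so one could say the test is implied. It has no outcome, covariates, contrasts or multiplicity rule and is not listed afterwards, so it is not a prespecified test of the hypothesis.

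The authors also chose clustering on purpose and call it the main objective. That stands. A reader might infer that a linear model should become primary and clustering a descriptive second step. The documents do not support that, because it would replace the authors' design. Adding a model beside the clustering closes the gap.

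A reader might further infer that the crosstab will miss condition-specific differences almost entirely. That holds only for narrow profiles on correlated scales. The Aims expect a rise in trauma and sensitization in all three conditions together with specific traits and defenses. For that pattern the crosstab loses power but is well above chance, and when every score shifts it does at least as well as the direct tests.

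Finally, that the crosstab is cluster by diagnosis is an inference. The planned group of cluster analyses within the study samples could even mean clustering inside each diagnosis, and then no such table would exist. What can be shown is that the test is not specified.

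**Conclusion.** The gap can be read from the text and rests on no simulation: the hypothesis and the sample size concern diagnoses, and no listed analysis compares diagnoses on the Aim 1 scores. If the crosstab is cluster by diagnosis, it is an indirect test that cannot locate a difference by score and condition.

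The size of its power loss is conditional. The documents give no correlations, profile widths or effects per score, so only the range across the patterns tabulated above can be given, from near chance to no loss.

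A reader might also infer from the mismatch that the study is too small. It is not: with 0.35 read as Cohen's f, 432 is four times what the stated inputs require, and it is ample for adjusted comparisons by diagnosis.

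This should be fixed. It does not undermine the study, since the missing model needs only data that will be collected anyway. What would be lost without the change is its prespecification.

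**What to change.** In the statistical section:

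1. Keep the cluster analysis as the main exploratory aim.
2. Beside it, prespecify a MANOVA or linear models with diagnosis (four levels) and named covariates for the Aim 1 scores, as the test of the Aims hypothesis. Include contrasts of each condition with controls and between conditions, with Holm adjustment.
3. Name both margins of the crosstab, and say whether clustering is run on the pooled sample or within each diagnosis.
4. Restate the power for the diagnosis model: with 432 in total, 85% for f = 0.170 at alpha 0.05 and f = 0.224 at 0.05/22. State the effect-size metric, and correct the derivation, which gives 108 in total if 0.35 is Cohen's f.
5. Give the crosstab's detectable w separately: 0.17, 0.19 and 0.20 for 2, 3 and 4 clusters.

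The cost is a change of wording, one more set of models and a multiplicity adjustment over the Aim 1 scores. No further participants or data are needed. The change should be dated before the scores are analysed.
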